6.3.2 Follow-Up Visits

Follow-up visits will occur at 2 weeks, 6 weeks, 3 months, and then every 3 months for the remainder of the study duration period (minimum of 12 months and a maximum of 24 months). All study visits will be completed within a ± 1-week window. The following assessments will occur at each follow-up study visit.

- Focused interval history and physical examination
- CV medication history
- Document rationale for changes in HF therapy
- Serum creatinine, BUN, and electrolytes (local laboratory)
- NT-proBNP (local laboratory, Biomarker-guided Arm only)
- QOL questionnaire (as described in 6.7)
- Medical resource use and cost assessment
- Ascertainment of interval safety events and endpoints
- Biomarker collection for biorepository (as described in 6.4)

Subjects in the biomarker-guided arm will have NT-proBNP testing performed in the local laboratory by appropriately trained personnel, and these values will be used for the purposes of titrating therapy to the

protocol-specified target. If therapy is adjusted, the changes in therapy and the rationale for the adjustment (e.g. clinical reason, not at biomarker target) will be recorded on the eCRF. Subjects in the usual care arm will not have routine assessment of natriuretic peptides except for compelling medical reasons.

6.3.3 Follow-up Assessments after Adjustment of Therapy or Hospitalization

There will be a 2-week (± 1 week) reassessment for patients who have a change in therapy, resulting from clinical findings or natriuretic peptide levels. **This follow up can be in person or a remote laboratory evaluation at the discretion of the treating physician**. This follow-up assessment will include a brief clinical assessment (if in person visit), measurement of renal function and electrolytes, and local laboratory NT-proBNP measurement (biomarker-guided arm only. Follow-up assessments will continue every 2 weeks until therapeutic targets are reached, or the investigator determines that further titration of therapy is not possible. Patients hospitalized for HF during the study will have a 2-week follow-up study visit post discharge to reassess and adjust medical therapy, which will include all standard follow-up assessments as defined above (Section 6.3.2).

6.4 Biorepository and Core Lab Biomarker Assessment

Local laboratory NT-proBNP values will be used to adjust therapy in patients randomized to the biomarkerguided arm. Additionally, at each regular study visit, all subjects (regardless of treatment arm) will have blood samples sent to the Biomarker Core Laboratory for the central blinded assessment of NT-proBNP levels. Data from this core lab assessment will not be provided to the sites but will be used to standardize assessments for all study patients (including those in the usual care arm) during data analysis at the completion of the study. As a quality control measure, the correlation between local site laboratory NTproBNP values and central core lab NT-proBNP values will be assessed after enrollment of the first 100 patients, and as needed thereafter.

Additional plasma, serum, and DNA samples (once only) will be collected and stored in the GUIDE-IT biorepository at each regular study visit (see Schedule of Assessments). Individual study subjects will be permitted to opt out of the biorepository while still participating in the main trial, but participation in the biorepository for all subjects will be strongly encouraged. Samples will be collected, processed, and labeled at the study site and shipped to the biorepository as described in the Manual of Operations. These biorepository samples will be used by GUIDE-IT investigators to evaluate the role of specific "biomarkers" (including genetic biomarkers) in the biology and pathophysiology of HF and the biology of the response to biomarker-guided therapy. A Biomarkers and Genetics Committee will establish and manage the process for scientific review of proposals to use these biologic samples.

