2.6 Design of GUIDE-IT: Rationale for Using NT-proBNP and Specific Target

Both BNP and NT-proBNP are widely clinically available and both markers have been used in previous trials of biomarker-guided therapy. We have selected NT-proBNP as the biomarker to be used for guiding therapy in the intervention arm of the GUIDE-IT study. The half-life of NT-proBNP is substantially longer than that of BNP (6 hours vs. 20 minutes), suggesting it is preferable for long-term therapeutic monitoring over time. For this reason, more prior studies have used NT-proBNP rather than BNP. NT-proBNP performed better in predicting long-term morbidity and mortality in a head-to-head comparison in Val-HeFT. Finally, the data supporting the validity of a specific natriuretic peptide target are stronger for NT-proBNP than for BNP.

Several lines of evidence have led us to select an absolute NT-proBNP target rather than a percentage change. First, the use of specific targets for physiologic parameters is standard in the management of other

cardiovascular diseases such a hypertension, hyperlipidemia, and diabetes. A strategy of targeting a specific percentage reduction may leave patients with elevated baseline values with a target that is still associated with substantial risk. The rationale for specific cut points is strongest if there is evidence for specific inflection points in the association of continuous physiologic parameters with risk. Data from the PRIDE study strongly suggests the presence of such a cut-off at approximately 972 pg/mL of NT-proBNP (Figure 4) 17 . Similarly, in an analysis of VAL-HeFT, the optimal cut point of NT-proBNP to define increased risk was 1078 pg/mL. Finally, as described above the interim results from the PROTECT pilot study demonstrated a strong signal for efficacy using an NT-proBNP target of 1000 pg/mL.³² The consistency of these findings around an NT-proBNP threshold of ~1000 pg/mL has led us to target that level of NT-proBNP suppression for GUIDE-IT.

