3.2 Planned Number of Subjects and Centers

The planned enrollment for the GUIDE-IT study is approximately 1,100 subjects at approximately 40 centers in North America. To maximize generalizability, centers outside of North America may be considered for participation if HF management is sufficiently similar to U.S. practice and appropriate use of guideline-based therapy can be verified.

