5. STUDY INTERVENTIONS

GUIDE-IT will randomize patients in a 1:1 allocation to either:

- Biomarker-guided arm (approximately 550 subjects): Titration of HF therapy with a goal of achieving and maintaining a target NT-proBNP < 1000 pg/mL OR
- Usual care (approximately 550 subjects): Titration of HF therapy based on target doses from current evidence based guidelines

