5.1 Biomarker-guided Arm

In the Biomarker-guided arm, NT-proBNP values from the local clinical laboratory will be utilized by treating physicians for the purpose of achieving at NT-proBNP target of < 1000 pg/mL. The GUIDE-IT protocol will specify interventions to be considered to achieve the NT-proBNP target in the biomarker-guided arm, but specific treatment decisions will be at the discretion of the treating physician. The order of implementation will be based on clinical judgment, and more than one intervention can occur in a single encounter. Titration of neurohormonal antagonists will be emphasized over titration of diuretics except in the case of clinically apparent congestion or in the case of very high NT-proBNP levels, which usually indicate subclinical volume overload. Specific changes in therapy and the rationale for them (e.g., in response to clinical change or NT-proBNP levels) will be captured on the eCRF. Potential interventions to decrease NT-proBNP levels will include:

- Up-titrate or add Angiotensin Converting Enzyme (ACE)-inhibitor or ARB
- Up-titrate or add beta-blocker (if not clinically congested)
- Up-titrate or add hydralazine-nitrates in African-American patients
- Increase loop diuretic dosage (if clinically congested or NT-proBNP > 5000 pg/mL)
- Up-titrate or add spironolactone if tolerated by renal function and potassium
- Add oral thiazide diuretic
- Add digoxin
- Consider adding ARB to ACE-I (if not on spironolactone)
- Consider hydralazine-nitrates in non-African-American patients
- Intensified or repeated heart failure education regarding diet, sodium restriction, etc.
- Consider optimization of cardiac resynchronization therapy (if CRT device implanted)
- Reconsider potential indications for CRT (if not previously implanted)
- If in atrial fibrillation, maximize rate control or consider more aggressive attempts at normal sinus rhythm
- Consider exercise training or cardiac rehabilitation

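### The named check of local against core-lab NT-proBNP is a correlation, which cannot show a calibration bias around the absolute 1000 pg/mL target

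*Protocol*

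**What the plan says.** The intervention works against a fixed number. Protocol section 5 defines the guided arm as "Titration of HF therapy with a goal of achieving and maintaining a target NT-proBNP < 1000 pg/mL", and section 2.6 explains the choice: "Several lines of evidence have led us to select an absolute NT-proBNP target rather than a percentage change". Section 5.1 says whose measurement counts: "NT-proBNP values from the local clinical laboratory will be utilized by treating physicians". Section 6.6 expects investigators to act on above-target values even when symptoms and signs have not worsened.

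Section 6.4 adds a central blinded measurement on every patient at each regular visit: "Data from this core lab assessment will not be provided to the sites but will be used to standardize assessments for all study patients". It then sets out one direct comparison of the two sources. As quality control, "the correlation between local site laboratory NTproBNP values and central core lab NT-proBNP values will be assessed", timed "after enrollment of the first 100 patients, and as needed thereafter". The section states no type of coefficient, no acceptance limit, and no measure of bias or agreement.

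Section 9.3 separately plans to compare distributions of selected variables across sites and to investigate non-random deviations. It does not name NT-proBNP.

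**The concern.** With an absolute target, what matters in a local assay is whether it puts a patient on the same side of 1000 pg/mL as the reference. Correlation measures how tightly two sets of readings follow a straight line, whatever its slope and intercept. A laboratory that reads consistently high or low still follows such a line.

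At stake is delivery of the strategy under test. If local readings are shifted, the effective target differs from the one in the protocol. Guided patients whose true level lies between the nominal and effective targets are managed as if they were on the other side. A site could follow the protocol faithfully on a shifted number. The core-lab values cannot undo this at analysis, because the titration has already happened.

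**Working it through.** The protocol gives no figure for this check, so there is nothing to reproduce. The first result needs no assumptions. The others do.

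**1. Common shift (exact).** For k > 0, corr(a + kX, Y) = corr(X, Y). Any shift shared by all samples leaves r where it was.

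**2. Effective target.** If the local laboratory reads k times the core lab, a local 1000 corresponds to a core value of 1000/k: 1429 (k = 0.7), 1250 (0.8), 833 (1.2) and 769 (1.3).

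**3. Misclassification at 1000 pg/mL.** Assumptions, none from the documents: core values log-normal, median m = 1500 to 2500 pg/mL, log-SD s = 1.0, random error of 10% in the local reading, k as shown.

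Ignoring random error, the share of samples on different sides is |Φ(ln(1000/(k·m))/s) − Φ(ln(1000/m)/s)|. For m = 2000 and k = 0.8 this is Φ(−0.470) − Φ(−0.693) = 0.319 − 0.244 = 0.075. Simulation with the random error included gives, across the range of m:

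| k | r | On different sides of 1000 | Truly below, read above | Truly above, read below |
|---|---|---|---|---|
| 1.0 | 0.99 | 2-3% | 4-6% | 1-2% |
| 0.8 | 0.99 | 7-9% | <0.1% | 8-13% |
| 1.2 | 0.99 | 4-6% | 19-24% | <0.1% |
| 1.3 | 0.99 | 6-9% | 26-33% | <0.1% |

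The less favourable case k = 0.7 gives 11-14% overall, again with r about 0.99. At m = 2000, additive shifts from −300 to +300 pg/mL also leave r at 0.992.

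**4. Laboratories that differ from each other.** Here r does move. Let the local factor vary between sites with log-SD d. On the log scale, r ≈ s/√(s² + 0.10² + d²). With s = 1.0:
- d = 0.1: 1/√1.02 = 0.990
- d = 0.2: 1/√1.05 = 0.976
- d = 0.3: 1/√1.10 = 0.953

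On the raw scale, simulating 100 patients over 40 sites with m = 2000 gives average pooled r of about 0.985, 0.964 and 0.932. If one site of 40 reads 30% low, log-scale r moves from 0.995 to 0.993. A fall of this kind gives neither direction nor size and does not identify the laboratory.

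**5. What the same pairs could show.** Appendix A has a local NT-proBNP and a core sample for both arms at day 0, so 100 patients can supply about 100 pairs. The 95% CI half-width of the mean log ratio is 1.96·σ/√100, which is 0.0196 for σ = 0.10 and 0.0392 for σ = 0.20, or about 2% to 4%. A common shift of 10% to 30% would be plain.

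**6. By laboratory at the first look.** Section 3.2 plans "approximately 1,100 subjects at approximately 40 centers in North America". If spread evenly, 100/40 = 2.5 patients per site, and the half-width becomes 1.96 × 0.10/√2.5 = 0.124 or, for σ = 0.20, 0.248. That is too wide to judge one laboratory. Guided patients add a pair at each regular visit, so this improves with time.

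**The case against.** Several points against the concern are sound, and they limit it.

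- **Core-lab values are not held back until the end.** They stay hidden from sites, but the quality-control comparison uses them during the trial. The pairs that would reveal a bias are collected throughout. Only the named summary of them is weak.
- **Other surveillance exists.** The cross-site comparison in section 9.3 might pick up an outlying laboratory. It does not name NT-proBNP, and differences in case mix would confound it, so it does not replace a paired comparison.
- **No pass mark is stated.** A reader might infer that a miscalibrated site would pass the check. The protocol gives no criterion to pass. Limits and triggers may well sit in a laboratory manual or the analysis plan, and their absence here is not the point. The word correlation may also be loosely meant. Still, it is the measure the protocol fixes, and nothing in the text gives it another meaning.
- **The band of affected patients is narrow.** For a 30% high reading, the affected true values lie roughly between 769 and 1000 pg/mL. The 19-24% figure for a 20% high reading applies only to the minority truly below target and must be read against 4-6% with no bias.
- **Treatment does not follow mechanically from 1000 pg/mL.** Section 5.1 leaves decisions to the treating physician. Section 2.6 derives the target from cut points of 972 and 1078, so it is approximate. Section 2.7 reports high within-patient variability at low levels.

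What remains is that the stated statistic does not measure the property an absolute target depends on, and that a better one is available from the same data.

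**Conclusion.** The point holds as a minor improvement. Correlation is the only direct local-to-core measure named in section 6.4. It is blind to a common shift and responds only modestly to differences between laboratories, so it cannot give the size, direction or source of a calibration bias relative to 1000 pg/mL.

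Under the assumptions above, a shift of 20% either way or 30% high takes overall misclassification from about 2-3% to about 4-9%, with r still about 0.99. The 30% low case reaches 11-14%. These percentages depend on an assumed distribution and assumed shifts. The documents report no assay bias, and none is alleged. The invariance of r to a common shift needs no such assumption.

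Two stronger readings are tempting and are not supported. One is that the trial could not discover a miscalibrated laboratory: it holds the paired data needed to do so. The other is that the primary result would be invalid. The primary comparison is by intention to treat on centrally adjudicated events, with the committee blinded to arm (sections 6.5, 8.7 and 8.8), so a shift does not affect type I error. It can only reduce fidelity to the strategy. No effect on power or on the hazard ratio has been shown.

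**What to change.** In section 6.4, replace or supplement the correlation with an agreement analysis on the same paired samples:

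- the mean log ratio of local to core values with its 95% CI;
- limits of agreement on the ratio scale;
- the percentage of pairs classified differently at 1000 pg/mL.

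Report these overall and by assay platform after the first 100 patients. Report them by laboratory later, as repeat-visit pairs accrue, allowing for several pairs from one patient. Set in advance the ratio that triggers follow-up with the local laboratory.

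The cost is one or two sentences in the protocol and a little more analysis. It needs no new samples or visits, no release of core-lab values to sites, and no change to how patients are treated.

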6.5 Minimizing Potential Bias

To address potential effects of an unblinded trial design on outcome determination, we have chosen an objective primary endpoint (HF hospitalization or CV death) and will use a blinded Clinical Endpoints Committee (CEC) to classify potential endpoints. Source data (i.e., history, laboratory procedures and discharge summaries) on all deaths and hospitalizations will be reviewed by the CEC in a consistent, standardized and unbiased manner. Final cause for each event will be adjudicated using definitions that will be established in the CEC Charter.

Another potential source of bias relates to the possibility that the greater frequency of medical visits due to natriuretic peptide guidance will lead to improved patient outcomes through a mechanism other than

biomarker-guided titration of HF therapy. While GUIDE-IT will mandate frequent visits in the usual-care group (as consistent with standard practice), any observed differential in the number of medical interventions (driven by out-of-range natriuretic peptide levels in apparently stable patients) may be the mechanism by which any treatment effects are realized. The alternative of mandating extra clinical visits for the usual-care arm to mirror the visit pattern of the biomarker-guided arm carries risk of biasing the trial results. Those extra visits, which would not occur in regular clinical practice, could lead to extra testing and treatment modifications that result in the outcomes of the two arms converging, thus masking a real treatment benefit. While there is no perfect solution to this problem, we will have detailed data on the content of each clinic visit in both treatment arms; thus, we will determine how often these visits included significant modifications of medical therapy.

6.6 Maximizing Protocol Adherence

In order to persuasively test the primary hypothesis of GUIDE-IT, we will maximize adherence to the assigned strategies. In the case of the biomarker-guided arm, the investigators will act on above-target NT-proBNP levels even in the absence of worsening symptoms or signs of HF. Similar to studies of intensive glycemic control or blood pressure control, adherence monitoring and feedback to providers will be critical to the success of GUIDE-IT. To ensure that investigators adhere to the protocol, GUIDE-IT will convene an Adherence Committee to focus on investigator education and training.

Based on our experience in prior studies to identify and correct non-adherence, adherence monitoring and intervention will take a stepped approach. For example, the clinical coordinating center (CCC) will collect patient feedback on adherence. Investigators at sites with two episodes of non-adherence will be contacted to review episodes and the importance of adherence will be reemphasized. Reports on adherence will be provided to the Executive Committee. The Executive Committee will consider suspending enrollment at sites not performing at appropriate levels. Adherence performance will be used in determining authorship of trial manuscripts. Although we recognize that such substantial efforts at ensuring investigator adherence are not practical in all real-world settings, we believe they are critical for a proof-of-concept efficacy trial such as GUIDE-IT.

6.7 Quality of Life Assessments

GUIDE-IT will use a battery of validated instruments that build on a disease-specific core, supplemented by generic measures to provide a comprehensive assessment of health related QOL. These assessments of quality of life (QOL) will be performed at baseline by site coordinators and then 3 months, 6 months and annually to a maximum of 24 months by structured telephone interview conducted by the EQOL CC staff. A detailed description of each of these instruments with instructions will be included in the Manual of Operations. Assessments at each visit will include the following:

- Kansas City Cardiomyopathy Questionnaire (KCCQ)
- Duke Activity Status Index (DASI)
- enter for Epidemiological Studies Depression Scale (CES-D)
- Medical Outcomes Study Short Form (SF-12)
- Medical Outcomes Study Short Form (SF-36) subscales: General Health, psychological well-being, vitality, social functioning)
- EQ-5D

6.8 Economic Data Collection Procedures

Total medical costs can be divided into five major components: inpatient hospital care, inpatient physician care, outpatient (ED visits, observational stays, rehabilitation stays, nursing home stays) physician care,

outpatient testing, and outpatient medications. Hospital costs will be calculated using hospital billing data, with charges converted to costs using the departmental charge-to-cost conversion factors available from each hospital's annual Medicare Cost Report. Physician costs (both inpatient and outpatient) will be estimated by mapping major procedures and physician services recorded on the case report form and hospital bills to appropriate current procedural terminology (CPT) codes in the Medicare Fee Schedule. Outpatient medication costs will be based on the *Drug Topics Red Book* average wholesale price, discounted as appropriate to reflect market acquisition costs. Outpatient testing costs will be assigned using the Medicare Fee Schedule for the physician component and the Medicare ambulatory payment classification (as per rates for the institutional and laboratory component).

Hospital bills for patients in the U.S. (detailed, summary ledger, and UB-04) will be collected by the GUIDE-IT EQOL CC staff after discharge from the hospital This process typically starts with a call to the head or the representative of the given hospital's patient accounting department to request the bill, and is followed by a written letter including a copy of the signed consent form if requested. Once received, in order to maintain confidentiality, the patient's name will be removed and replaced with the GUIDE-IT patient study number and patient initials before further processing.

In addition, cost-to-charge ratios (Medicare Cost Report Worksheets C and D-1, Part 2) will be obtained for each hospital where a GUIDE-IT hospitalization is reported. These reports can be obtained from the hospital in question, the Medicare Intermediary for that region, or the Centers for Medicare and Medicaid Services. Reports will be obtained for each year of study enrollment and follow-up up to the most recent report available at the start of the data analysis phase.

6.9 Removal or Replacement of Subjects

Subjects have the right to withdraw from the study at any time and for any reason without prejudice to his or her future medical care. In the case of subject withdrawal, the investigator will discuss with the subject the most appropriate way to terminate study participation to ensure the subject's health. All efforts will be made to complete and report the observations as thoroughly as possible up to the date of study termination. Randomized subjects who withdraw from the study will not be replaced.

